To assess group differences in the number of weeks of abstinence in the follow-up period (Aim-2a), a Poisson regression model was fit with the total number of weeks of self-reported abstinence in the four-week follow-up period as the dependent variable and treatment, site, and treatment by site interaction as independent variables. We conservatively imputed missing values as non-abstinent, thereby including the total ITT sample. We additionally performed a sensitivity analysis for weeks of abstinence by including the weeks preceding the 9th rTMS-treatment visit and immediate post-visit since these two weeks represent the time following the delivery of a total of 16-sessions of rTMS (a similar dose to early rTMS for depression studies). We calculated the relative risk of having a week of abstinence as a measure of the effect size, along with 95% confidence intervals. We used creatinine-corrected urine cannabinoids to verify self-reported abstinence at follow-up weeks 2 and 4, and calculated the proportion that these two methods were concordant.

To evaluate group differences in the number of days of cannabis use (Aim-2b), we utilized a GLMM with the number of days-per-week of cannabis use as the dependent measure. We included participants in the model who had follow-up data (the completer sample; N=51) and given the apparent divergence in days-per-week of cannabis use in the final two-weeks of the follow-up period, we chose to focus our analysis on that period.

Residual normality was assessed for each of the above models using QQ-plots. We included sex in all models to detect a potential effect, but when no significant effects were found, we excluded sex from the subsequent final models. Apart from craving, this was a pilot trial and not powered a priori to detect statistically significant differences; however, statistically significant *p*-values are noted when observed. When reported, a level of $\alpha = 0.05$ was used (two-tailed), and no adjustments for multiple comparisons were made for this preliminary investigation. Effect sizes at each time point were estimated as Cohens d using means and pooled standard deviations. Statistical analyses were conducted using R software (version 4.2.1, GNU project) and SAS version 9.4 (Cary, NC).

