Aim 2: Determine if a course of excitatory rTMS applied to the DLPFC reduces cue-reactivity in reward network structures during a validated fMRI paradigm. We hypothesize that as compared to participants receiving sham rTMS, participants receiving active rTMS will have a reduced percent signal change in BOLD response in reward structures during a validated cue-reactivity fMRI paradigm following their final rTMS session as compared to prior to their first rTMS session.

Exploratory Aim: Determine if participants receiving active rTMS have a higher rate of abstinence following treatment as compared to participants receiving sham rTMS. We hypothesize that participants receiving active rTMS will be more likely to be abstinent over the final two-weeks of the study period than participants receiving sham rTMS. We will define abstinence as no self-reported cannabis use over the final two weeks of the study, and a ratio of four week to two-week creatinine corrected urine THCCOOH of < 0.5 (10-12).

B. BACKGROUND AND SIGNIFICANCE

Cannabis Use Disorder (CUD) is a common and escalating problem in the United States. The prevalence of CUD more than doubled between 2001-2002 and 2012-2013 (1). Coinciding with the high prevalence of CUD, there has been a high demand for treatment. According to SAMHSA, in 2014 over one million individuals sought treatment for CUD(2). In recent years it has become increasingly clear that those desiring to quit cannabis are rarely able to do so on their own and suffer from a clear withdrawal syndrome(13). Currently available treatments have low long-term success rates(14-17). There has subsequently been significant interest in the development of new treatment options for those individuals with CUD who desire to stop using.

Repetitive transcranial magnetic stimulation (rTMS) is a non-invasive brain stimulation technique that is able to alter cortical excitability and is FDA-approved to treat Major Depressive Disorder. Magnetic fields pass unimpeded through the scalp, skull and meninges, and can directly excite cortical areas. High frequency rTMS (greater than 5 pulses per second) increases cortical excitability(18). Single sessions of rTMS induce temporary changes; however, multiple sessions can induce more long-term changes.

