General Overview (Figure 3): The primary aims are to determine the efficacy of 20 sessions of DLPFC rTMS in decreasing cannabis cue-induced craving (Aim 1) and cue reactivity in a validated fMRI paradigm (Aim 2). The aims of the study will be accomplished by performing a double-blind, randomized, sham controlled clinical trial with two arms. Individuals with CUD will be

recruited from the community. All participants will receive a three-week behavioral intervention and adjunctively undergo a course of either *active* or *sham* rTMS during that time. Post-treatment

outcomes will be assessed at two- and four- weeks following completion of the rTMS course.

Screening: Participants will meet with study personnel either in person, or via Stanford Secure Zoom, and complete

assessments about substance use, psychiatric and medical history. Eligible participants will complete questionnaires and provide a urine sample for drug screening. For females, a pregnancy test will be done prior to the drug screen. Pregnant women will not be allowed to participate.

rTMS Sessions: rTMS will be delivered via a MagPro double blinded rTMS Research System (MagVenture, Denmark) with a Cool-B65 Butterfly Coil (a combined active and sham coil). We will use a standard resting motor threshold (rMT) determination to determine the TMS dose (42). Treatment will be delivered at 120% rMT. Each active rTMS study-treatment will consist of a total of 4000 pulses of 10Hz stimulation (5s-on,10s-off). Treatments will be delivered at the EEG coordinate for F3 (which approximates the left DLPFC), and will be found using the Beam-F3 method (43). This is a treatment paradigm that has been used extensively in other trials (25, 44-46). Sham sessions will be delivered using an electronic sham system consisting of a coil that mimics the appearance and sound of rTMS, combined with a TENS device which produces a small electric shock mimicking the feeling of active rTMS. This type of sham has been demonstrated to be indistinguishable from active rTMS, has been well tolerated in (21, 25), and successfully used in other clinical trials(47, 48).

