Statistical Analysis: Baseline demographic and clinical measures will be compared across treatment groups using standard statistical methods (i.e., categorical variables compared using Pearson chi square test of independence; continuous variables compared using univariate ANOVAs). Characteristics that display imbalance at the baseline measure, association with the dependent variable, or are known to be predictive of cue induced craving, reactivity, or cannabis-use outcomes will be assessed for inclusion as covariates in the final models. To test our primary hypothesis that a full course of active excitatory rTMS will reduce cue induced craving as compared to sham rTMS (Aim 1), generalized linear mixed effects models will be constructed to estimate treatment group differences in craving scores. Overall statistical significance for the effects of treatment group, time, and their interaction will be assessed using a likelihood ratio test that compares the final model, to a model consisting of an intercept term alone. The hypothesis that those receiving active rTMS will have decreased craving will be tested using model-based estimates to construct group level comparisons across all the planned time points. Normality of residuals will be tested for these models and when found in error, appropriate transformations or non-parametric methods will be conducted. For Aim 2 (evaluating the impact of rTMS on cannabis CR), BOLD response during the cannabis cue vs. neutral cue trials will be the primary contrast of interest to test hypotheses. Where significant differences are observed, parameter estimates from task-based models, from each ROI will be extracted and relations with clinical endpoints examined. For our exploratory Aim: The primary analysis will involve preliminarily investigating the efficacy of active rTMS, compared to sham rTMS in increasing the proportion of cannabis abstinent participants during the final two weeks of study treatment (four-week follow-up). A combination of self-reported abstinence from

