compensated at the end of each visit, and thus will receive pro-rated compensation as they complete the study.

There will be no additional compensation for those choosing to receive open label treatment following the experiment.

b. Sources of Materials

Assessments:

Data collection:

Schedule of visits and assessments and Data Collection:

	Assessment domain	Screen	Baseline	Final rTMS Visit	2-week F/U	4-week F/U
Screening and Enrollment Eligibility:						
MINI International Neuropsychiatric Interview (MINI) for the DSM-5 (54): Structured interview to determine DSM-5 based psychiatric conditions.	Psychiatric history	X				
Urine Pregnancy Test (bHCG)	Pregnancy status	X				
Hamilton Rating Scale for Depression 24-Item (HRSD₂₄)(55): Clinician administered measure of depressive symptoms.	Depressive symptoms	X		X	X	X
The Cannabis Use Disorder Identification Test-R (CUDIT-R)(56): Validated measure assessing severity of disordered cannabis use.	Severity of Cannabis Use	X				
Cannabis Cue-Induced Craving (Aim 1): Primary outcome: Change in MCQ score during cannabis cue paradigm. Secondary outcome: Average weekly change in MCQ assessed during each TMS treatment session.						
The Marijuana Craving Questionnaire (MCQ) (57): Validated measure of cannabis craving. Collected before and after each cannabis cue exposure.	Provoked Cannabis Craving		X	X	X	X
Activation of Reward Structures (Aim 2): Primary outcome: Percent signal change in BOLD response during cue-reactivity fMRI paradigm.						
Substance Use Outcomes (Exploratory Aim): Primary outcome: Number of participants who are abstinent by TLFB for the last 2 weeks of the study with a ratio of four-week to two-week creatinine corrected urine THCCOOH of <0.5. The THCCOOH ratio is able to accurately predict no new cannabis use (10-12).						
Secondary outcomes: change in a) creatinine corrected cannabis level (ng/ml) and; b) subjective use measured by TLFB (number of days used per week and number of cannabis use sessions per week).						
Time Line Follow Back (TLFB) (58): Calendar-based instrument designed to assess substance use.	Self-Reported Substance Use	X	X	X	X	X
Urine Drug Test with Creatinine Corrected Cannabis Level (Collected on the 1st, 5th and 10th rTMS visit, and at follow-up visits)	Objective Substance use	X	X	X	X	X

Delayed Discounting Task (67): Participants choose between receiving hypothetical money immediately or more money if they wait longer.	Cognitive Control		X	X		

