4. RISK BENEFIT ASSESSMENT FOR THE PROPOSED RESEARCH

All of the procedures we will perform as part of this trial are low-risk, and each said risk has been minimized. Each participant will receive a standard of care behavioral treatment for Cannabis Use Disorder, and a promising candidate-treatment. We subsequently believe that the risk-benefit ratio is favorable for each individual participant. We also believe the data obtained in this trial has the potential to benefit society by developing this candidate-treatment.

5. DATA AND SAFETY MONITORING PLAN This section is based on the recommendations in NIDA's "Guidelines for Developing a Data and Safety Monitoring Plan" (www.drugabuse.gov/funding/dsmbsopt.html). A detailed DSMP will be developed and approved by NIH program staff prior to study initiation.

a. Summary of the Protocol.

This application proposes to investigate the effects of rTMS on craving and cannabis use in Cannabis Use Disordered participants. The primary outcomes of interest are cannabis cue induced craving (Aim 1), and cue reactivity in reward network areas (Aim 2). Inclusion/exclusion criteria are outlined above. Power calculations and sample sizes are in the Data Analysis Plan section above.

b. Trial Management.

The study will be managed from the Brain Stimulation Lab within the Department of Psychiatry and Behavioral Sciences at Stanford University. The target population is described above in the inclusion/exclusion criteria.

c. Data Management and Analysis.

Data will be entered by research team-members directly into REDCap, and fMRI data will be kept on secure Stanford servers.

d. Quality Assurance.

We will conduct quarterly data audits. Confidentiality protections are outlined above.

e. Regulatory Issues.

Potential conflicts of interest will be reported using the NIH rules for disclosure. Adverse Events (AEs)/Serious Adverse Events (SAEs) occurring during the course of the project will be collected, documented,

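### The SAP omits the protocol's primary fMRI aim without explanation and gives its number to cannabis-use outcomes from the protocol's exploratory domain

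*SAP*

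**What the plan says.** **Protocol (combined document, 2021).** The General Overview in section D gives the primary aims as efficacy in "decreasing cannabis cue-induced craving (Aim 1) and cue reactivity in a validated fMRI paradigm (Aim 2"). The Data and Safety Monitoring Plan, item a, says the same of outcomes: "The primary outcomes of interest are cannabis cue induced craving (Aim 1), and cue reactivity in reward network areas (Aim 2"). Section A defines Aim 2: "Determine if a course of excitatory rTMS applied to the DLPFC reduces cue-reactivity in reward network structures during a validated fMRI paradigm". Its hypothesis there is a lower percent signal change with active than with sham stimulation, after treatment relative to before. For the analysis, the Statistical Analysis section says: "BOLD response during the cannabis cue vs. neutral cue trials will be the primary contrast of interest to test hypotheses". The Sample Size Justification gives Aim 2 its own statement: d of 0.7 to 0.8, two-sided 5%, 36 randomised per arm, power above 80%.

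Cannabis use has a different status. Section A has "Exploratory Aim: Determine if participants receiving active rTMS have a higher rate of abstinence following treatment as compared to participants receiving sham rTMS". The schedule of assessments has "Substance Use Outcomes (Exploratory Aim): Primary outcome: Number of participants who are abstinent by TLFB for the last 2 weeks of the study", with a four-week to two-week urine ratio below 0.5 also required. As a secondary outcome under the same heading it lists "subjective use measured by TLFB (number of days used per week and number of cannabis use sessions per week").

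**SAP (June 27, 2023).** Aim-1 is craving. Then: "To assess group differences in the number of weeks of abstinence in the follow-up period (Aim-2a), a Poisson regression model was fit". Aim-2b is days of use per week, analysed by a mixed model. fMRI, BOLD, regions of interest and imaging do not appear. The closing paragraph says that, craving apart, the trial was a pilot without prospective power.

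**The concern.** The SAP is the later document and is written as an account of the analyses performed. If it governs reporting, one of the protocol's two primary outcomes is missing with no statement that it was dropped, not collected or kept for another report. A reader who matches aim numbers between the documents would take weeks of abstinence and days of use for the protocol's Aim 2.

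What is at stake is selective reporting. A primary outcome can go unreported while outcomes from the exploratory domain carry its label. Those outcomes are tested at an unadjusted 0.05. For Aim-2b, the SAP says the analysis was focused on the last two follow-up weeks because the arms appeared to diverge there, in the 51 participants with follow-up data. The power sentence adds to the problem, because it removes the trace that imaging was ever powered.

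**Working it through.** **1. Was Aim 2 powered in the protocol?** Inputs from the Sample Size Justification: n = 36 per arm, d = 0.7 to 0.8, two-sided alpha 0.05.

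Normal approximation: power = Φ(d·√(n/2) − 1.960), with √(36/2) = 4.243.

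- d = 0.7: 0.7 × 4.243 = 2.970; 2.970 − 1.960 = 1.010; Φ(1.010) = 84.4%.
- d = 0.8: 0.8 × 4.243 = 3.394; 3.394 − 1.960 = 1.434; Φ(1.434) = 92.4%.

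Two-sample t-test power is 83.4% and 91.7%. The protocol's claim of more than 80% reproduces, with no allowance for attrition. The SAP's statement that only craving was powered therefore contradicts the protocol.

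For context only: if the 25% attrition assumed for Aim 1 also applied to scans, 36 × 0.75 = 27 per arm would remain. The t-test power would then be 71.4% (d = 0.7) to 82.2% (d = 0.8). The documents do not report how many scans were obtained.

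**2. The aims side by side.**

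| Item | Protocol, 2021 | SAP, 2023 |
|---|---|---|
| BOLD cue reactivity | Aim 2, primary, powered | Not mentioned |
| Abstinence | Exploratory Aim: yes/no over the last two weeks, self-report plus urine ratio below 0.5, logistic regression | Aim-2a: count of self-reported abstinent weeks over four weeks, Poisson regression; urine used only for concordance |
| Days of use per week | Secondary outcome under the Exploratory Aim | Aim-2b, mixed model |
| Powered a priori | Craving and BOLD response | Craving only |

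The two use outcomes stand differently. Days per week is a protocol outcome that has lost its exploratory label. Weeks of abstinence is not a protocol outcome: window, form, urine criterion and model all differ from the protocol's abstinence endpoint.

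**3. Does the protocol fill the gap?** In part. Section A gives the comparison (active versus sham, before to after), the schedule gives the measure (percent signal change), and the task description and Statistical Analysis section give the contrast (cannabis versus neutral images). Cannabis minus neutral is the per-scan measure, and the section A hypothesis says how it is to be compared.

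What is missing is the model for that comparison: no group and time terms, no covariates, no list of regions and no rule for testing several regions. In the same section, Aim 1 gets a named model and a treatment-by-time interaction. The timing of the second scan also needs reconciling: section A places it after the final session, and the fMRI Paradigm section before the final treatment.

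**The case against.** The strongest defence is that the combined document is itself titled as a protocol and statistical analysis plan and covers Aim 2, so the gap lies in the later SAP and not in every document. That is right, and it limits the point. A reader might infer that no between-arm test of BOLD was ever intended, since the quoted contrast is within a scan. The documents do not support this: section A states the active-versus-sham hypothesis, and the sample-size text powers a treatment effect on BOLD. Nor do the primary outcomes as a whole lack a between-arm analysis, because craving has treatment-by-time models in both documents.

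The protocol's hierarchy is also mixed. Its introductory text ties the main goal to Aim 1 and describes Aim 2 as exploring mechanism, and the Statistical Analysis section reserves the primary hypothesis for Aim 1. No co-primary decision rule exists, so that term should not be used. But three other places give Aim 2 primary or powered status, so it cannot be dropped without comment.

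Finally, the SAP calls the trial a pilot and discloses that nothing was adjusted for multiplicity. That softens its claims, but it discloses neither the omission nor the relabelling.

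**Conclusion.** The point holds. Followed as written, the 2023 SAP leaves one of the protocol's two primary outcomes without analysis or explanation, gives its aim number to two cannabis-use outcomes, and contradicts the protocol on power (above 80% claimed; 83.4% to 91.7% recomputed under the protocol's own assumptions). No numerical effect on a result can be given, because the documents contain no imaging data.

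Two further inferences should be resisted. One is that imaging results exist and were withheld: the documents only plan the scans and do not say whether they were acquired, abandoned or reserved for a separate report. The other is that two protocol outcomes were promoted. Only days per week is a protocol outcome. Abstinence was already an aim, though an exploratory one, and its endpoint was replaced.

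**What to change.** In the SAP:

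- Restore protocol Aim 2 and state what happened to it.
- If scans were acquired, compare percent signal change (cannabis minus neutral) at the second scan by arm, adjusted for first-scan value and site, in named reward regions. Report it whatever the result. Because the SAP is already in the past tense, mark this model as specified after the protocol and do not call it planned.
- If scans were not acquired, or only some were, report the number obtained and the reason.
- Relabel weeks of abstinence and days of use as exploratory, and disclose that weeks of abstinence replaced the protocol's two-week yes/no endpoint with its urine criterion and logistic regression.
- Correct the power sentence to agree with the protocol's Sample Size Justification.

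The cost is SAP text and, if scans exist, one small model per region. The drawback is that if scans are missing, the comparison rests on fewer participants than were randomised.

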Sample Size Justification: The primary focus of this study is to show evidence, with sufficient strength, that treatment with active rTMS will result in decreased cue induced craving (Aim 1), and decreased BOLD response in reward network structures during a cue-reactivity fMRI paradigm (Aim 2) in CUD participants treated with either active or sham rTMS. For Aim 1: Within subject craving measures tend to be highly correlated when measured closely in time and thus we assume a conservative ICC of $p=0.75$ (previous CUD studies range $p=0.60-0.75$) with a standard deviation of ≈ 12.2 . We intend to detect a clinically meaningful craving score difference between the two treatment groups of 8.5 (Cohen's $d=8.5/12.2\approx 0.7$). This is a conservative estimate given that recent multi-session rTMS treatment trials have yielded larger effect sizes on craving ($d=0.98$ (7) in alcohol users, and $d=0.84$ (9) in cocaine users). In the proposed study we will measure increased craving (via MCQ total score) following the presentation of a validated cannabis cue paradigm both before and after a treatment course of rTMS. Under the assumption of independent observations, a total sample size of 32 participants equally allocated to each treatment assignments will provide 80% power with a type 1 error rate of 5% to detect the stated effect size of 0.7. However, the effective sample size in a repeated measures data setting is reduced when assuming an ICC of 0.75. The number of participants per group required is therefore estimated to be $n=27$. Additionally, we need to adjust for study attrition between randomization and the 4-week follow up visit. Assuming an attrition rate of up to 25%, a sample size of **36 participants randomized to each treatment group (n=72 total)** will provide adequate power to detect the primary aim effect size of $d=0.7$ between those receiving active and sham rTMS. **For Aim 2:** In a within subjects investigation of nicotine use disordered participants undergoing a single session of rTMS, there was a significant effect on BOLD response to smoking cues (see figure 2, Preliminary Studies section). If we assume that, as with previous study of cue induced BOLD reactivity in smokers using rTMS, our effects are of medium to large size (e.g. $d=0.7-0.8$) with alpha =5% (2-tailed), a sample of **36 randomized participants in each group will result in greater than 80% power for detecting effects of treatment on CR-BOLD response**. In sum, we are confident that the proposed randomized sample size of 72 participants will be sufficient to test Aims 1 and 2. **For our exploratory Aim**, our recent, non-contingency management based medication trials for cannabis cessation have shown varying placebo abstinence rates (defined as ≤ 50 ng/ml THCCOOH UCT) at the end of study (EOS) treatment (5-15%) (38, 39, 41). Since we are only hoping to provide preliminary data to power a more definitive study, our sample is not designed to sufficiently answer this question definitively. Despite this fact we will still have power to detect a large effect on abstinence. An rTMS abstinence rate of at least 30% greater than placebo at the end of study treatment under the most conservative conditions, at a 10% placebo abstinence rate, a randomized sample size of 36 participants in each treatment group will provide 80% power with a type 1 error of 5% to detect this difference at the end of this pilot study.

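### Aim-2a fits a Poisson model to 0–4 abstinent weeks and names no variance estimator or dispersion check; default standard errors would understate the variance if a person's weeks are positively correlated and about a quarter of participants are imputed to zero

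*SAP*

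**What the plan says.** In its Aim-2a paragraph the SAP states that "a Poisson regression model was fit with the total number of weeks of self-reported abstinence in the four-week follow-up period as the dependent variable" and lists "treatment, site, and treatment by site interaction as independent variables". On missing data it says: "We conservatively imputed missing values as non-abstinent, thereby including the total ITT sample". The effect measure follows two sentences later: "We calculated the relative risk of having a week of abstinence as a measure of the effect size, along with 95% confidence intervals". A sensitivity analysis extends the total to six weeks: "We additionally performed a sensitivity analysis for weeks of abstinence by including the weeks preceding the 9th rTMS-treatment visit and immediate post-visit".

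The only diagnostic is in the SAP's closing paragraph: "Residual normality was assessed for each of the above models using QQ-plots". No standard-error type (model-based, scaled or sandwich), dispersion statistic or fallback model is named.

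The protocol's Statistical Analysis section does not fill the gap, because it planned logistic regression for a yes/no abstinence endpoint. The SAP describes every outcome except craving as not powered in advance. The protocol's Sample Size Justification says that the sample cannot settle the abstinence question.

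**The concern.** A Poisson model with default standard errors assumes that the variance of the count equals its mean. Here the count is the sum of four weekly yes/no outcomes from one person, and two forces pull the variance in opposite directions. A bounded total of independent weeks has variance below its mean, so the interval would be too wide. Correlation between one person's weeks, and people fixed at zero by imputation, push the variance above the mean, so the interval would be too narrow. A QQ-plot of residual normality does not check either.

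At stake are the RR interval and any p-value noted with it. The SAP notes significant p-values when observed, without multiplicity adjustment, and the protocol wants these data to help power a larger trial. The RR estimate itself and the craving outcome are not affected.

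**Working it through.** **Plan's own figure.** None is given for the Poisson model. The nearest is the protocol's 80% power for the yes/no endpoint (10% vs 40%, 36 per group). An exact two-sided Fisher calculation gives 80.0%, so that figure reproduces and is not in question.

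**Inputs.**
- From the documents: N = 72, four follow-up weeks, two-sided alpha 0.05, treatment-by-site model.
- *z*, participants who are all-zero through imputation: not stated for Aim-2a. The protocol's planning says "we need to adjust for study attrition between randomization and the 4-week follow up visit. Assuming an attrition rate of up to 25" per cent, and 0.25 × 72 = 18. For Aim-2b the SAP says "We included participants in the model who had follow-up data (the completer sample; N=51", and 72 − 51 = 21 if that count also applies to Aim-2a.
- *p*, weekly abstinence among the others: assumed 10–30%, with 5% as a check. The protocol's 5–15% placebo abstinence is an end-of-study rate and only a rough guide.
- *c*, within-person correlation of weekly abstinence: not given, so a range is used.
- Site split: the protocol's enrollment section gives 43 + 28 = 71, so 43/29 is assumed to reach 72.

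**Variance formula.** With a share z/72 fixed at zero:
- mean = (1 − z/72) × 4p
- variance/mean = (1 − p)(1 + 3c) + 4pz/72

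Setting this to 1 gives the break-even correlation c* = p(1 − 4z/72) / [3(1 − p)].

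- z = 0: 0.1/2.7 = 0.037, 0.2/2.4 = 0.083 and 0.3/2.1 = 0.143 at p = 10, 20 and 30%. Below c* the interval is too wide.
- z = 18: 1 − 4 × 18/72 = 0, so c* = 0 for every p.
- z = 21: c* is slightly negative.

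Variance/mean:

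| p | z | c = 0 | c = 0.2 | c = 0.5 |
|---|---|---|---|---|
| 10% | 0 | 0.90 | 1.44 | 2.25 |
| 10% | 21 | 1.02 | 1.56 | 2.37 |
| 30% | 0 | 0.70 | 1.12 | 1.75 |
| 30% | 21 | 1.05 | 1.47 | 2.10 |

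**Type I error.** This was simulated with 20,000 replicates per setting, no treatment effect, beta-binomial weeks, the treatment-by-site model and an equal-weight average over sites. Imputed people were drawn at random, and fits with an empty cell were excluded. Ranges are over p = 10–30%, nominal 5%, model-based standard errors:

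| z | c = 0 | c = 0.2 | c = 0.5 |
|---|---|---|---|
| 0 | about 2–3% | about 6–8% | about 14–17% |
| 21 | about 3–5% | about 7–11% | about 12–18% |

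The low end of the last cell moves between 11.0 and 11.7% from run to run. HC1 sandwich errors (factor n/(n − 4)) give about 3–6% throughout. At p = 10% and z = 21, model-based error is still only about 5% at c = 0.1, because the counts are sparse.

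**Excluded fits.** At p = 10% and z = 21, 10% of fits (c = 0.2) to 28% (c = 0.5) have an empty treatment-by-site cell. At p = 5% and z = 21, model-based error is about 2% at c = 0.2 and 5% at c = 0.5, but about 50% and 73% of fits have an empty cell.

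**Illustration (invented counts).** Take 8 + 6 abstinent weeks by site on sham against 16 + 12 on active, with arms treated as equal in size within site. RR = 2.00 and SE(log RR) = 0.5 × √(1/8 + 1/6 + 1/16 + 1/12) = 0.331. The model-based interval is 1.05–3.82 (p = 0.036). With z = 21, weekly abstinence is 42/204 = 0.206:
- c = 0.2: ratio 0.794 × 1.6 + 0.240 ≈ 1.5, interval 0.90–4.42 (p = 0.087).
- c = 0.5: ratio 0.794 × 2.5 + 0.240 ≈ 2.2, interval 0.76–5.23 (p = 0.16).

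With z = 0 and independent weeks, weekly abstinence is 42/288 = 0.146 and the ratio is 0.85. The correct interval is then narrower than the model-based one, at 1.10–3.64.

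**Six weeks.** With none missing, variance/mean is (1 − p)(1 + 5c), so c* falls to p/[5(1 − p)] = 0.022, 0.050 and 0.086.

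**The case against.** The SAP is a short summary in the past tense and names no standard-error type for any model. A relative risk from Poisson regression is often obtained with a robust variance, and the text does not say outright that the RR and its interval come from this fit. A reader might infer that the reported interval is wrong, or certainly too narrow. The documents do not support that: they do not show that model-based errors were used, and with few all-zero people and nearly independent weeks the error runs the other way.

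The size also rests on assumed inputs. A reader might put the protocol's ICC of 0.75 in for *c*, but that figure is for craving scores. A reader might take 21 as the Aim-2a count of all-zero participants, but it comes from the Aim-2b completer sample. The illustration starts at p = 0.036, so modest widening crosses 0.05; it shows what can happen, not what is likely.

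The sparse-data objection stands in full. Near 5% weekly abstinence, inflation is negligible among estimable fits, and the interaction model often cannot be estimated, which a sandwich variance does not cure.

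The unknown correlation is not a reason to leave the method as it is. For p of 10–30% the sandwich error is near nominal on both sides of the break-even, so the choice need not wait for *c*.

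**Conclusion.** The point holds as a conditional one. The SAP leaves open how the Aim-2a interval is computed, and the default for the model it names is doubtful for this outcome. If the RR interval comes from that fit with model-based errors, and z is near 18–21, any positive within-person correlation makes variance exceed the mean. For p of 10–30% and z = 21, type I error among estimable fits is then about 7–11% at c = 0.2 and 12–18% at c = 0.5. With no all-zero people the break-even correlation is 0.04–0.14, and below it the interval is too wide. At p = 5% non-estimability matters more.

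The values of *p*, *c* and *z*, the 43/29 split, random imputation across arms and the site-averaged contrast are all assumptions. The outcome is exploratory and unpowered, so this is worth fixing but does not threaten the trial's main result.

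**What to change.** Compute the Aim-2a RR interval and p-value from the model already specified, with participant-level sandwich standard errors and a small-sample correction (HC1, for example) in place of model-based ones. Do the same for the six-week sensitivity analysis. Report the Pearson dispersion statistic, the number of participants set to all-zero, and any empty treatment-by-site cell. State that the RR comes from this fit and how it combines sites. If robust errors were already used, say so and add those figures.

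The cost is one variance option, a few reported numbers and a sentence or two of SAP text, with no new data and no change in model terms. The interval will usually be somewhat wider: in the simulations with z = 21, by a factor of 1.14–1.21 on the log scale at c = 0.2 and 1.35–1.46 at c = 0.5. It would be narrower if weeks prove nearly independent and few people are all-zero.
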